### 7.4 Exploratory Variables

Plasma and serum samples will be collected at specified times and may be used to evaluate the effect of tenapanor alone and in combination with sevelamer on PTH, CRP, aldosterone and other cardio-renal biomarkers (These data may not be part of the study report.)

Protocol No.: TEN-02-401

Edition No.: 1

Future exploratory research on serum/plasma biomarkers may be performed related to cardio-renal disease and/or mineral metabolism or that may influence the response (i.e. distribution, metabolism, safety, tolerability, and efficacy) to tenapanor. (These data will not be part of the study report.).

### 8 METHODOLOGY/STUDY VISITS

### 8.1 Baseline, Visit 1

Prior to enrollment, the Investigator will inform each prospective patient of the nature of the study, explain the potential risks, and obtain written informed consent from the patient prior to performing any study-related procedures.

No baseline assessments will be performed as part of this protocol; all baseline data for TEN-02-401 will be taken from the TEN-02-301 End of Treatment (EOT) visit and will consist of the following:

- Informed consent
- Inclusion and exclusion criteria (Section 5)
- Weight (pre-dialysis)
- Kt/V (most recent measurement prior to enrolling into TEN-02-401)
- Medical history (major medical conditions taken from TEN-02-301)
- Phosphate binder used and dose
- KDQoL survey
- DSI survey (for English speakers only)
- Physical examination (Section 7.2.2)
- Vital signs (pre-dialysis) (Section 7.2.3)
- ECG evaluation (Section 7.2.4)
- Clinical laboratory tests (pre-dialysis) (Section 7.2.5)
  - Serum chemistry
  - Hematology
  - o Coagulation profile (if applicable)
- Serum pregnancy test, if applicable
- FGF-23, and exploratory biomarker sample (pre-dialysis)
- Dispense study drug

Protocol No.: TEN-02-401

Edition No.: 1

- Begin collecting adverse events
- Review concurrent medications

# 8.2 Weeks 1, 2, 3, 4, 6, and 8, Visits 2, 3, 4, 5, 6, and 7

- Serum phosphorus (pre-dialysis)
- Return/accountability of study drug
- Dispense study drug
- Adverse event reporting
- Review concurrent medications

# 8.3 Months 3, 6, 9, 12, and 15, Visits 8, 9, 10, 11, and 12

- Weight (pre-dialysis)
- Kt/V (most recent measurement prior to screening)
- KDQoL survey (not Months 9 and 15, Visits 10 and 12)
- DSI survey, for English speakers only (not Months 9 and 15, Visits 10 and 12)
- Vital signs (pre-dialysis) (Section 7.2.3)
- Clinical laboratory tests (pre-dialysis) (Section 7.2.5)
  - Serum chemistry
  - o Hematology
  - o Coagulation profile (if applicable)
- FGF-23, and exploratory biomarker sample (pre-dialysis)
- Return/accountability of study drug
- Dispense study drug
- Adverse event reporting
- Review concurrent medications

# 8.4 Months 4, 5, 7, 8, 10, 11, 13, 14, 16, 17, Telephone Visit T1, T2, T3, T4, T5, T6, T7, T8, T9, T10

- Adverse event reporting
- Review concurrent medications

Protocol No.: TEN-02-401

Edition No.: 1

#### 8.5 Month 18, Visit 13; End of Treatment Visit

- Weight (pre-dialysis)
- Kt/V (most recent measurement prior to screening)
- KDQoL survey
- DSI survey (for English speakers only)
- Physical examination (Section 7.2.2)
- Vital signs (pre-dialysis) (Section 7.2.3)
- ECG evaluation (Section 7.2.4)
- Clinical laboratory tests (pre-dialysis) (Section 7.2.5)
  - Serum chemistry
  - Hematology
  - o Coagulation profile (if applicable)
- Serum pregnancy test, if applicable
- FGF-23, and exploratory biomarker sample (pre-dialysis)
- Return/accountability of study drug
- Adverse event reporting
- Review concurrent medications

#### 8.6 Unscheduled Visits

Unscheduled visits, for missed scheduled visits or safety or tolerability related reasons are allowed. Procedures performed are at the discretion of the Investigator.

#### **8.7** Withdrawal Procedures

In the event of a patient's withdrawal, the Investigator will make every effort to complete all assessments performed at End-of-treatment visit (Visit 13). Withdrawn patients will be followed until resolution of any AEs or until the unresolved AEs are judged by the Investigator to have stabilized.

For the withdrawal criteria see Section 5.3.

Protocol No.: TEN-02-401

Edition No.: 1

#### 8.8 Total Blood Volume Required for Study

**Table 8-1:** Approximate Blood Volume per Completed Patient

Test	No. of Samples	Volume (mL)	Total (mL)
Hematology (blood)	7	3	21
Chemistry (serum) (includes serum pregnancy test)	7	7	49
Phosphorus (serum)#	6	5	30
iFGF-23 (plasma)	7	4	28
Exploratory biomarker sample (serum and plasma)	7	13	91
Coagulation (plasma)	7	3	21
Total Volume			240

# Separate sample is only taken at specified times when no chemistry sample is taken

#### **8.9** Protocol Deviations

Patients must fully meet the following criteria in order to enroll in the study. In keeping with regulatory requirements, Ardelyx does not grant protocol waivers to inclusion/exclusion criteria.

A protocol deviation is defined as any intentional or unintentional change to, or noncompliance with, the approved protocol procedures or requirements. Deviations may result from the action or inaction of the patient, Investigator, or site staff. Examples of deviations include, but are not limited to:

- Failure to adhere to study exclusion and inclusion criteria
- Failure to comply with dispensing or dosing requirements
- Missed or out-of-window visits
- Failure to adhere to test requirements, including vital signs, laboratory tests, physical
  examinations, medical history; either tests not done, incorrect tests done, or not done
  within the time frame specified in the protocol
- Procedural deviations such as incorrect storage of study drug, failure to update the ICF when new risks become known, failure to obtain Institutional Review Board (IRB) approvals for the protocol and ICF revisions

A process for defining and handling protocol deviations will be established. Protocol deviations that effect the safety of a patient require immediate notification of the Medical

Protocol No.: TEN-02-401

Edition No.: 1

Monitor and Sponsor. The Investigator is responsible for seeing that any known protocol deviations are recorded and handled as agreed.

### 9 STATISTICAL CONSIDERATIONS

### 9.1 Statistical Analysis Plan

A formal statistical analysis plan (SAP) will be provided separately. If the language in this protocol and the language in the SAP differ, the SAP governs. If additional analyses are performed or changes are made to the planned analyses after unblinding of the study data, such deviations will be documented in the clinical study report.

# 9.2 Determination of Sample Size

Approximately 150-200 patients with ESRD on hemodialysis (HD) or peritoneal dialysis (PD) will be enrolled in this study. The sample size of this study is not planned based on statistical considerations.

#### 9.3 Analysis Sets

Two analysis sets are defined for this study: Safety Analysis Set and Full Analysis Set (FAS).

#### **Safety Analysis Set:**

All patients who receive at least one dose of study drug (tenapanor or sevelamer) in the study. The safety analysis set will be used for the analysis of safety variables.

#### **Full Analysis Set:**

All patients who meet the study entry inclusion/exclusion criteria, receive at least one dose of study drug (tenapanor or sevelamer), and have at least one post-baseline sP assessment in TEN-02-401. The FAS will be used for the analysis of efficacy variables.

#### 9.4 Statistical Methods

### 9.4.1 General Approach

Unless specified otherwise, descriptive statistics including the number of observations, mean, standard deviation, median, minimum, and maximum will be presented for continuous variables. Frequency and percentage of patients will be presented for categorical variables.

Protocol No.: TEN-02-401

Edition No.: 1

## 9.4.2 Baseline Descriptive Statistics

Baseline characteristics, including demographics, disease characteristics, prior/concomitant medications, and medical/surgical history will be summarized by TEN-02-301 treatment arm and overall for each analysis set.

#### 9.4.3 Efficacy Analysis

All efficacy variables will be descriptively summarized at each visit for the FAS and each TEN-02-301 treatment arm (tenapanor or sevelamer). Descriptive summaries of sP variables will also be repeated for FAS subjects with a baseline sP >4.5 mg/dL.

For response endpoints, the response rate at each post-baseline visit will be estimated with asymptotic 95% confidence interval (CI) for each TEN-02-301 treatment arm. Inferential analyses of sP endpoints will be performed for comparisons of phosphorus-lowering effect between monotherapy (tenapanor and sevelamer alone) and combination therapy (tenapanor combined with sevelamer) unless the sample size in each monotherapy treatment group is less than 15. Detailed model specifications will be provided in the statistical analysis plan (SAP). Inferential analyses of other endpoints may be performed as suggested by the data.

Analyses will be detailed in the statistical analysis plan (SAP).

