# 1.2 Synopsis

**Protocol Title:** A Long-Term, Open Label Study to Evaluate the Ability of Tenapanor

Alone or in Combination with Sevelamer to Treat to Goal Serum Phosphorus in Patients with End-Stage Renal Disease on Dialysis

(NORMALIZE).

**Sponsor:** Ardelyx, Inc.

**Study Phase:** Phase 3

**Objectives:** The primary objective of this study is:

• To evaluate the ability of tenapanor alone or in combination with sevelamer to achieve serum phosphorus concentration (sP) within the population reference range (sP ≥2.5 and ≤4.5 mg/dL) in patients with end-stage renal disease on dialysis with hyperphosphatemia (>4.5 mg/dL).

The secondary objectives of this study are:

- To compare the phosphorus lowering effect of tenapanor and sevelamer alone in patients with sP >4.5 mg/dL to patients treated with a combination of tenapanor and sevelamer.
- To evaluate the effect of tenapanor alone and in combination with sevelamer on the proportion of patients reaching serum phosphorus targets defined as ≤4.5 mg/dL.
- To evaluate the effect of the addition of tenapanor to patients taking sevelamer on the percentage reduction in the sevelamer dose
- To evaluate the effect of tenapanor alone and in combination with sevelamer on intact fibroblast growth factor 23 (iFGF23).
- To evaluate the effect of tenapanor alone and in combination with sevelamer on the Kidney Disease Quality of Life (KDQoL) survey.
- To evaluate the effect of tenapanor alone and in combination with sevelamer on the Dialysis Symptom Index (DSI) survey (for English speakers only).
- To compare the long-term safety of tenapanor alone and in combination with sevelamer.

The exploratory objectives of this study are:

- To evaluate the effect of tenapanor alone and in combination with sevelamer on PTH, CRP, aldosterone and other cardio-renal biomarkers (These data may not be part of the study report.)
- To collect and store plasma/serum for future exploratory research into serum/plasma biomarkers related to cardio-renal disease and/or mineral metabolism or that may influence the response

Protocol No.: TEN-02-401

Edition No.: 1

(i.e. distribution, metabolism, safety, tolerability, and efficacy) to tenapanor. (These data will not be part of the study report.)

**Number of Sites:** 40-60 clinical sites in the US

Number of Patients Approximately 150-200 patients with ESRD on hemodialysis (HD) or

peritoneal dialysis (PD).

Study Design Patients who complete the TEN-02-301 study (PHREEDOM) may be

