# **Efficacy Analyses:**

All efficacy variables will be descriptively summarized at each visit for the FAS and each TEN-02-301 treatment arm (tenapanor or sevelamer). Descriptive summaries of sP variables will also be repeated for FAS subjects with a baseline sP >4.5 mg/dL.

For response endpoints, the response rate at each post-baseline visit will be estimated with asymptotic 95% confidence interval (CI) for each TEN-02-301 treatment arm. Inferential analyses of sP endpoints will be performed for comparisons of phosphorus-lowering effect between monotherapy (tenapanor and sevelamer alone) and combination therapy (tenapanor combined with sevelamer) unless the sample size in each monotherapy treatment group is less than 15. Inferential analyses of other endpoints may be performed as suggested by the data.

Analyses are described in Section 9 and will be detailed in the statistical analysis plan (SAP).

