#### 4 STUDY DESIGN

# 4.1 Design Summary

Patients who complete the TEN-02-301 study (PHREEDOM) at Visit 23, may be eligible to enroll into TEN-02-401 (NORMALIZE).

Patients will be required to sign an ICF and meet all inclusion and no exclusion criteria. No baseline assessments will be performed as part of this protocol; all baseline data for TEN-02-401 will be taken from the TEN-02-301 End of Treatment (EOT) visit. Patients from the

Protocol No.: TEN-02-401

Edition No.: 1

TEN-02-301 tenapanor arm will either receive only tenapanor or be given sevelamer in addition to tenapanor based on their sP following a protocol-specified dose titration schedule. Patients from the TEN-02-301 sevelamer arm will be given tenapanor in addition to their sevelamer dose and the sevelamer dose will then be adjusted based on their sP following a protocol-specified dose titration schedule. Patients will be monitored for safety and efficacy with in-office and telephone visits for up to an additional 18 months.

All study visits must be scheduled after a short dialysis interval (only for HD patients; e.g., Wednesday or Friday for patients on a MWF schedule and Thursday or Saturday for patients on a TThS schedule). Body weight and blood collections for laboratory assessments **must** be performed pre-dialysis. All other assessments may be performed pre-, during, or post-dialysis but should be performed at the same time at each visit. For patients receiving PD, visits should be performed on the same day each week, if possible.

Investigators may decrease or increase the dose of tenapanor based on sP levels and/or GI tolerability. The changes must be made in 10 mg increments to a minimum of 10 mg BID or a maximum of 30 mg BID. The dose of sevelamer carbonate may be adjusted based on the guidance provided in Section 4.1.1 or the sevelamer package insert. Investigators have flexibility to dose sevelamer, TID, BID or QD based on their experience with each patient or as per package insert.

Laboratory efficacy endpoints will be assessed at various times throughout the study; sP will be measured at every visit.

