#### 6.1.3 Dose Adjustments

All patients in the tenapanor group will start at the dose that they were receiving at the end of the TEN-02-301 study. Dosing regimens can be adjusted based on the most recent sP laboratory data (central laboratory data or standard of care local laboratory data).

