#### **Sevelamer Arm**

If patients are from the TEN-02-301 sevelamer arm, tenapanor dose will be added based on their baseline sP as described below. Investigators may decrease or increase the tenapanor dose based on sP levels and/or GI tolerability in 10 mg increments to a minimum of 10 mg QD or a maximum of 30 mg BID, not more than once daily. Dosing regimens can be adjusted based on the most recent sP laboratory data (central laboratory data or standard of care local laboratory data).

- sP >2.5 and ≤3.5 mg/dL: add three 10 mg tablets of tenapanor QD and Sevelamer dose can be lowered by one 800 mg tablet TID.
- sP > 3.5 and  $\leq 4.5$  mg/dL: add three 10 mg tablets of tenapanor QD
- sP >4.5: add three 10 mg tablets of tenapanor BID

If sP >4.5 mg/dL at next visit

 add three 10 mg tenapanor tablets, if on QD regimen to a maximum of 30 mg tenapanor BID. If on 30 mg tenapanor BID follow sevelamer dose regimen changes described below

Sevelamer dose can be increased by at least one 800 mg tablet at the largest meal and up to one 800 mg tablet TID; Investigators have flexibility to dose sevelamer BID or QD based on their experience with each patient or as per package insert. If sP < 2.5 mg/dL at any visit:

Protocol No.: TEN-02-401

Edition No.: 1

Sevelamer dose can be lowered by one 800 mg tablet TID; Investigators have flexibility
to dose sevelamer BID or QD based on their experience with each patient or as per
package insert.

• If patient is not taking sevelamer then tenapanor dose can be lowered by one 10 mg tablet BID, unless already at tenapanor 10 mg BID, then can dose tenapanor 10 mg QD.

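### The planned inference against sevelamer alone has no concurrent comparison group, and the plan does not say what takes its place

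*Combined protocol and SAP*

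**What the plan says.** The first secondary objective (Synopsis 1.2 and section 3.2) is "To compare the phosphorus lowering effect of tenapanor and sevelamer alone in patients with sP >4.5 mg/dL to patients treated with a combination" of the two drugs. The Synopsis turns this into a commitment: "Inferential analyses of sP endpoints will be performed for comparisons of phosphorus-lowering effect between monotherapy (tenapanor and sevelamer alone) and combination therapy". Section 9.4.3 repeats it and adds a size rule, so that the comparison is of "monotherapy (tenapanor and sevelamer alone) and combination therapy (tenapanor combined with sevelamer) unless the sample size in each monotherapy treatment group is less than 15". Other inference is optional. Model details are left to the SAP, which governs under section 9.1.

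Treatment is set by previous arm and by sP:

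- **Former sevelamer arm (4.1):** "Patients from the TEN-02-301 sevelamer arm will be given tenapanor in addition to their sevelamer dose". Tenapanor may then be changed "in 10 mg increments to a minimum of 10 mg QD or a maximum of 30 mg BID" (6.1.3).
- **Former tenapanor arm (4.1):** patients "will either receive only tenapanor or be given sevelamer in addition to tenapanor based on their sP". On dose, 6.1.3 says "All patients in the tenapanor group will start at the dose that they were receiving at the end of the TEN-02-301 study". Its guidance adds no sevelamer from 2.5 to 4.5 mg/dL and adds it in every band above 4.5.
- **Allocation (6.1.4):** patients keep their TEN-02-301 group.
- **Baseline (7.2):** all values come from the TEN-02-301 end-of-treatment visit.

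**The concern.** This is the only between-regimen inference to which the plan commits. As worded, it names a sevelamer-alone group that the treatment rules do not create during the study. The objective also restricts attention to sP >4.5 mg/dL, the range in which the guidance moves former tenapanor patients onto combination. In the whole Full Analysis Set (FAS), the 4.5 cut that separates tenapanor alone from combination at entry is also the upper limit of the response endpoint in 7.3.

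Two things are at stake. A secondary objective might go unanswered, or be answered by a contrast that nobody specified in advance. And a difference produced by selection on baseline sP might be read as a difference between regimens.

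**Working it through.** The plan has no power or precision figure to reproduce. Section 9.2 says the 150-200 patients were not derived statistically, and the threshold of 15 has no stated basis.

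**Step 1. Entry regimen under the stated rules**

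| Previous arm | Baseline sP (mg/dL) | Regimen at entry |
|---|---|---|
| Tenapanor | 2.5 to 4.5 | tenapanor alone |
| Tenapanor | above 4.5 | combination (guidance) |
| Sevelamer | above 2.5, all bands | combination |

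Sevelamer alone is zero in every stated band. The tenapanor minimum is given as 10 mg QD in the sevelamer-arm rules and 10 mg BID in section 4.1. These should be reconciled, but both are above zero, so titration does not lead to sevelamer alone. The unplanned exceptions are patients who stop tenapanor and former sevelamer patients at or below 2.5, for whom no starting rule is given.

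**Step 2. Assumptions for sizes.** The documents give no sP means, SDs or arm split. I assume 75-130 former tenapanor and 50-100 former sevelamer patients, mean sP 4.5-5.5, and between-patient/visit-to-visit SDs of 0.8/0.9, 1.0/0.9, 1.2/0.9, 1.0/0.7 and 1.0/1.2 (total SD 1.20-1.56).

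**Step 3. Group sizes**

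- Tenapanor alone at entry, whole FAS: n × P(sP ≤4.5) = 15 to 65.
- Tenapanor alone with baseline sP >4.5: none if the guidance is followed. The share that must be left without sevelamer to reach 15 is 15 / (n × P(sP >4.5)) = 14% to 40%. Example: n = 100, mean 5.0, SD 1.35 gives 64.5 patients above 4.5, and 15/64.5 = 23%.
- Tenapanor-alone patients whose sP is above 4.5 at the first post-baseline visit: about 7 to 24 with zero drug effect. They are selected on the outcome.
- Former sevelamer patients at or below 2.5: about 0 to 10, none in the sP >4.5 population.

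**Step 4. Selection in the FAS with zero drug effect.** Take 100 former tenapanor and 75 former sevelamer patients, mean 5.0, SDs 1.0/0.9. The visit-to-visit correlation is 1.0²/(1.0² + 0.9²) = 0.552.

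- Mean baseline is 3.59 on tenapanor alone (35.5 patients) and 5.78 in former tenapanor patients above 4.5 (64.5 patients).
- Combination baseline = (64.5 × 5.78 + 75 × 5.0)/139.5 = 5.36, a gap of 5.36 − 3.59 = 1.77.
- Expected gap in level at the next visit: 0.552 × 1.77 = 0.98 mg/dL, combination worse.
- Expected gap in change: 0.448 × 1.77 = 0.79 mg/dL, combination better.

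Simulation over the assumed settings, including arm means up to 0.5 apart, gives 0.47-1.44 mg/dL worse on level and 0.44-1.34 mg/dL better on change.

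**Step 5. The threshold of 15.** With concurrent groups, if inference is dropped only when both monotherapy groups are below 15, it can run with no sevelamer-alone patients. If it is dropped when either is below 15, it is always blocked.

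**Step 6. The replacement estimate.** The 95% CI half-width is t × √2 × SD/√n. With visit-to-visit SD 0.9 it is 2.010 × 1.414 × 0.9/√50 = 0.36 mg/dL for n = 50 and 0.25 for n = 100 (0.20-0.48 for SD 0.7-1.2). Variation in drug response between patients would widen it. Regression to the mean in a subset above 4.5 is (1 − correlation) × total SD × inverse Mills ratio. The example gives 0.448 × 1.345 × 0.577 = 0.35 mg/dL of apparent fall with no drug effect, and the range is 0.14-0.74.

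**The case against.** The strongest reply is that section 9.4.3 never says the groups are concurrent. Every patient has a baseline on the previous regimen, after which the second drug is added for the former sevelamer arm and for former tenapanor patients above 4.5. Read within patient, both monotherapies are represented at baseline and the threshold of 15 could be met. That reading is open, and for sevelamer alone it is the only workable one. But the section speaks of treatment groups and does not state a before-after contrast, so the plan has to say so.

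Second, the objective does not say that sP >4.5 is read at baseline. A reader might infer that this population has no monotherapy patients, or that the inference can never run. The documents do not support either in general. Both need concurrent groups fixed at entry, the first also needs sP read at baseline, and the second also needs the threshold read as either group. The sevelamer rules are guidance, and some tenapanor-alone patients will exceed 4.5 later.

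Third, model specification belongs to the SAP. This stands for the FAS selection. A reader might infer from Step 4 that the planned analysis is biased, but the plan does not state the unadjusted pooled comparison. Baseline-adjusted ANCOVA within the former tenapanor arm, with groups fixed at baseline and a linear relation, was near nominal in simulation (bias within ±0.05 mg/dL, rejection 3-7%). It extrapolates across 4.5 when the guidance is followed, and it says nothing about sevelamer alone.

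The sevelamer-arm rules also foresee patients no longer on sevelamer ("If patient is not taking sevelamer then tenapanor dose can be lowered by one 10 mg tablet BID"), a second sP-driven route to tenapanor alone. With no sevelamer doses in the documents, its size cannot be given.

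**Conclusion.** The point holds in this form. Inference against sevelamer alone has no concurrent group by assignment. That follows from the text and needs no assumption about sP. The emptiness of tenapanor alone above 4.5 and the dilemma over the threshold are conditional on the readings named above. The selection figures are illustrative: they rest on assumed sP distributions, entry regimen, the first post-baseline visit and an unadjusted analysis. Their use is to show that, with no drug effect, the choice between level and change decides which regimen looks better.

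It would be wrong to infer that the study's main result is compromised. The primary objective and the response rates with 95% CIs by TEN-02-301 arm are untouched. This is one secondary objective that cannot be carried out as written against a concurrent group, and it should be corrected before analysis.

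**What to change.** No dosing change is needed. In the Synopsis, section 9.4.3 and the SAP:

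1. Replace the comparison with sevelamer alone by the within-patient change in sP from the TEN-02-301 end-of-treatment visit to one main visit named in advance (Week 8, for example; other visits supportive). Use all FAS patients from the sevelamer arm and give a 95% CI. Label it an uncontrolled before-after estimate that includes any permitted titration, and report sevelamer dose alongside.
2. Report as supportive, with a regression-to-the-mean caveat, the subset with baseline sP >4.5 and the matching before-after change in former tenapanor patients given sevelamer at entry.
3. Describe tenapanor alone against tenapanor plus sevelamer within the former tenapanor arm, with groups fixed at baseline. Any model-based contrast is baseline-adjusted and supportive.
4. Apply the size rule to each comparison separately: no inference if either group in that comparison has fewer than 15 patients.
5. Reword the first secondary objective in 1.2 and 3.2 to match: estimate the change in sP after tenapanor is added to sevelamer, and describe sP on tenapanor alone and on the combination.

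The cost is wording and different tables from data already collected. The sponsor gives up a between-group p-value against sevelamer alone. The main estimate is uncontrolled, covers the whole former sevelamer arm rather than sP >4.5 only, and describes the regimen as titrated. Permitted sevelamer reductions may understate the effect: under the Step 2 assumptions, 4-16% of the arm has baseline sP >2.5 and ≤3.5, where reduction at entry is allowed. Permitted increases would act the other way.
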